7.2 Baseline Testing/Prestudy Evaluation

Baseline Evaluations

Baseline evaluations determine if the participant is a fit candidate for study participation and establish the participant's health status before entering the study. Standard-of-care labs or procedures done prior to signing consent will qualify for these baseline evaluations (i.e. physical exams, routine labs, vital signs) provided they were obtained within 30 days of the participant's Day 1 dose of study agent. All baseline evaluations (including labs) must be completed before requesting randomization and dispensing study drug. An Eligibility Checklist will be provided by the CLO at study initiation to help determine if the participant is eligible for the trial. This document will need to be signed and submitted to the CLO at the time of randomization.

Baseline **cystoscopy** demonstrating a bladder tumor. The physician should assess if the bladder tumor is invasive or non-invasive. The baseline cystoscopy must be completed within 120 days of randomization.

At the screening/baseline visit, blood for pharmacokinetics may be collected before eligibility has been confirmed. However, if the participant is later found to be ineligible, the sample may not be used. If the participant is found to be ineligible, clearly document the destruction of the pharmacokinetic blood sample in the participant's research chart.

A review of the participant's **medical history** will be done within 30 days of randomization.

A **physical examination** must be performed within 30 days of randomization.

Performance Status, using the Karnofsky must be assessed

A review of **concomitant medications** will be done within 30 days of randomization.

Laboratory tests needed for eligibility are: WBC, platelets, hemoglobin, total bilirubin, AST, ALT, alkaline phosphatase, creatinine, sodium and potassium. All of these laboratory analyses must be completed within 30 days before randomization.

Women of child-bearing potential must have a negative pregnancy test within 30 days of randomization.

Plasma Pharmacokinetics - Levels of erlotinib and metabolites will be assessed for all participants.

International Prostate Symptom Score (I-PSS) – The participant will complete the survey within 30 days of randomization

Review of Study Participation and Study Calendar - The research staff should review the upcoming

study visits and procedures with the participant. The participant should be provided a study calendar to record any side effects and the time the participant takes their study medication. The participant should be strongly encouraged to contact the research staff with questions about study participation.

Randomization and Drug Request

Once the eligibility evaluations have been completed and the participant meets all of the inclusion criteria in section 4.1 and meets none of the exclusion criteria in section 4.2, then the participant may be randomized to the trial. Before the participant may be randomized, the Eligibility Checklist must be completed and signed. Refer to section 6.8 for specific instructions on participant randomization.

7.3 Evaluation During Study Intervention

Special Drug Dosing Procedures

The participant must be instructed to take the medication in the evening on an empty stomach (no food within two hours before ingestion and within one hour post-ingestion) on day 1, 8 and 15 with the scheduled surgery on day 16. To ensure compliance, participants will be instructed verbally and in writing to take 4 tablets from their dispensed bottle on the scheduled evenings (study days 1, 8, and 15).

Drug Dispensing

Study agent will be shipped to the PO on a per participant basis. The request to ship study agent will be sent by the CLO once a request for participant randomization has been received from the site and eligibility has been verified by the CLO (refer to section 6.8). The bottle of study agent shipped to the PO will be identified with the randomization number assigned to the participant. When the participant's study agent arrives at the PO it may be dispensed to the participant. If the institution requires a prescription for investigational agents, the site coordinator or pharmacy staff must clearly document that all prescription procedures were followed before drug was dispensed to the participant.

Reminder Phone Contact Before Day 8 Visit

Approximately twenty four to seventy two hours before the Day 8 Visit, the participant will be contacted by phone and reminded about their Day 8 appointment time. The participant will also be reminded about study dose (timing, any dose modifications, how to take it, etc.).

Day 8 Visit*

Participants will be seen and evaluated by research staff on day 8 prior to ingesting their day 8 study dose. The evaluation includes vital signs, review any adverse events that took place including an assessment of toxicities (especially skin toxicity and diarrhea) and concomitant medications. Blood for safety labs and pharmacokinetics will be obtained. The coordinator should collect and calculate study drug compliance. If dose modifying toxicity (as described above) has occurred, study staff will instruct the participant on their modified study dose (3 tablets) for day 8 and 15. After completion of this assessment the day 8 study dose will be taken as instructed.

*Day 8 clinic visit is optional. If participant decides to opt out; a Day 8 phone call to evaluate safety assessments will be required. This phone call should occur after the day 8 dose is taken and within 48 hours of the dosing. The call should include an evaluation of toxicities, a review of concomitant medications and compliance.

Reminder Phone Contact Before Surgery

Approximately twenty four to seventy two hours before surgery or cystoscopy with biopsy, the participant will be contacted by phone and reminded about their last study dose (timing, any dose modifications, how to take it, etc.) and returning any leftover study medication and study medication bottles to the research

staff. The participant will also be reminded about the appointment(s) on the day of surgery with study staff.

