3. SUMMARY OF STUDY PLAN

Protocol chairperson: [name] FACS, University of Wisconsin

Primary Endpoint: The primary objective is to determine if there is a difference in EGFR phosphorylation in normal appearing bladder epithelium adjacent to tumor approximately 9-18 hours post-study dose, between patients randomized to erlotinib weekly as compared to placebo.

The prioritized secondary objectives are: 1) to assess the tolerance of high dose weekly erlotinib compared to placebo. 2) to assess the expression of phosphorylated EGFR in tumor tissue when available. 3) to assess the expression of e-cadherin and Ki67 in normal and abnormal urothelium. 4) to assess the expression of phosphorylated ERK in normal and abnormal urothelium. 5) to assess limited

pharmacokinetics of weekly erlotinib. 6) to assess the expression of p53 in normal and abnormal urothelium. 7) to assess the expression of let-7 in normal and abnormal urothelium. 8) perform an exploratory assessment of men on whether urination symptoms alter while on study.

Study Schema:

This is a multi-center, phase IIa randomized, double-blind, placebo-controlled study. Participants will be randomized on a 1:2 ratio to placebo vs. active study agent and stratified according to planned surgery (TURBT vs. cystectomy) and use of agents that significantly decrease Erlotinib bioavailability (tobacco, protein pump inhibitors). Fifteen participants will be enrolled on the placebo arm. A maximum of 30 participants will be enrolled on the active intervention arm. The accrual goals account for an anticipated dropout rate of 5-10%. Total anticipated accrual is therefore 45 participants.

There will be six sites participating in the study. Each randomized patient will be treated with study medication weekly x 3 doses. We will allow for study duration of approximately 3 years.

- Placebo or
- Erlotinib (with allowance for a 50% dose reduction for adverse events as specified in section 5.6)

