5.2 Study Agent Administration

The study agent (erlotinib or placebo) will be dispensed by an investigational pharmacist or appropriate study staff at the participating organization (PO) and then self-administered by the participant at home. A single bottle containing 16 tablets of study agent will be dispensed. If the participant is unable to return to the institution to pick up their study agent, the agent will be mailed to them via courier.

The study agent must be taken on an empty stomach (at least two hours after last eating). After taking their dose of study agent the participant must wait an hour before eating anything.

On Day 1, the participant will take one dose, 600 mg erlotinib or placebo in the form of four 150 mg erlotinib or matching placebo tablets by mouth in the evening (unless otherwise directed) on an empty stomach. All 4 tablets comprising a single dose of study agent will be taken together at the same time.

On Day 8, the participant will take their second dose of study agent (600 mg erlotinib or placebo in the form of four 150 mg erlotinib or matching placebo tablets) on an empty stomach as instructed either in the clinic following the collection of blood samples for pharmacokinetics or at home. Prior to the Day 8 Optional Visit/Mandatory Safety Assessment Phone call, the participant will receive a reminder phone contact instructing the participant when to take the Day 8 dose.

On Day 15 the participant will take their third dose of study agent approximately 9-18 hours before their scheduled surgery (600 mg erlotinib or placebo in the form of four 150 mg erlotinib or matching placebo tablets). The participant will receive a reminder phone contact prior to their final study dosing day instructing them when to take this final dose.

If surgery is delayed beyond the 16th day but less than the 23rd day, delay administration of the third dose until approximately 9-18 hours prior to the surgery. If surgery is delayed to day 23 through day 28, administer the third dose at day 15, and the fourth dose approximately 9-18 hours before surgery. If

surgery is delayed beyond day 28 (four weekly study drug doses), the patient will be considered not evaluable for the primary endpoint.

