5.6 Dose Modification

Study drug will be dose reduced (by 50%) from 4 tablets to 2 tablets for any of the following events:

- A grade 1 rash or diarrhea that the study subject finds unacceptable and desires the 50% dose reduction.
- A grade 2 skin toxicity
- A grade 2 diarrhea that does not respond to Imodium
- Any toxicity or adverse event \geq grade 3
- MD discretion for side effects assessed as at least possibly related to the study drug and for which the study subject finds unacceptable and desires the 50% dose reduction

Subjects that meet the above dose modification criteria even after a dose reduction will not receive any further doses. At the first report of grade 1 or 2 skin toxicity, subjects should be instructed on using the dispensed topical ointments (1% Clindamycin, 1% hydrocortisone): apply twice daily (not at the same time) each ointment to the affected area only. Subjects who report grade 1 or 2 diarrhea likely to be attributable to study drug should be instructed to use loperamide (Imodium) 2 mg after each loose stool. Provide participants with a copy of Appendix B.

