5.7 Adherence/Compliance

5.7.1 Compliance (tablet ingested/tablet instructed to take) will be assessed, but only subjects who take all study drug weekly for 3 doses (or 4 doses due to surgery delay) will be evaluable for the primary endpoint.

5.7.2 Compliance will be assessed via subject questioning, returned tablet count and planned drug levels.

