13. STATISTICAL CONSIDERATIONS

13.1 Study Design/Endpoints

This is a Phase IIa randomized, placebo-controlled, double-blind cancer chemoprevention trial of modulation of EGFR phosphorylation and other intermediate endpoint biomarkers by intermittent erlotinib in subjects with bladder cancer. Because there is a potential for a number of patients to be placed on a reduced dose of 300 mg/week because of intolerance to drug due to acne, in order to retain sufficient accrual at the 600 mg dose level, participants will be randomized in a 1:2 ratio of placebo to 600mg erlotinib administered weekly for 3 doses with the last dose approximately 24 hours of TURBT or cystectomy.

The primary endpoint for modulation of intermediate endpoint biomarkers will be the EGFR phosphorylation in normal appearing bladder epithelium adjacent to tumor 9-18 hours post-study dose; it is hypothesized that erlotinib will inhibit EGFR phosphorylation.

The secondary endpoints as prioritized include tolerance of high dose weekly erlotinib compared to placebo, EGF receptor phosphorylation in neoplastic bladder epithelium 9-18 hours post-study dose, the expression of e-cadherin and Ki67, the expression of phosphorylated ERK in normal and abnormal urothelium, limited pharmacokinetics of weekly erlotinib, the expression of p53 in normal and abnormal urothelium, and the expression of let-7 in normal and abnormal urothelium.

The primary analysis will be an as-randomized comparison of EGFR phosphorylation in bladder epithelium between the two randomized arms, based on two-sample t-test with normalizing transformation if necessary or Wilcoxon rank-sum test.

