13.4 Primary Objective

The primary objective is to determine if there is a difference in EGFR phosphorylation in normal appearing bladder epithelium adjacent to tumor approximately 9-18 hours post-study dose, between patients randomized to erlotinib weekly as compared to placebo. The primary endpoint of the study is EGFR phosphorylation in bladder epithelium at the end of study (weekly for 3 doses) in subjects with bladder cancer. For the primary comparison the difference between the placebo group and the erlotinib group will be tested as-randomized using a two-sample t-test with normalizing transformation if necessary or Wilcoxon rank-sum test.

Because of the required dose modification to 300 mg for grade 2 rash or diarrhea and allowed dose modification for grade 1 rash/diarrhea if subject prefers (refer to section 5.6) there is the potential for a number of patients to reduce dose at some point in the study. In addition, prior research has shown that smokers and those that regularly take proton pump inhibitors metabolize erlotinib faster, tolerating

erlotinib better, but gaining fewer benefits, effectively receiving a reduced dose compared to non-smokers and those that are not taking proton pump inhibitors (refer to section 2). As a supporting analysis for the primary endpoint we will explore a relationship for EGFR phosphorylation with a measure of dose received, and accounting for smoking status and proton pump inhibitor use.

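### Section 7.3 tells Day 8 staff to give a reduced dose of 3 tablets (450 mg), but the dose-modification rule in Section 5.6 requires 2 tablets (300 mg)

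*Combined protocol and SAP*

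**What the plan says.** The full dose is four 150 mg tablets, 600 mg, once weekly (Section 5.1). Five places then describe the reduced dose.

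- Section 5.6, the dose-modification rule: "Study drug will be dose reduced (by 50%) from 4 tablets to 2 tablets for any of the following events". The listed events include grade 2 skin toxicity and any event of grade 3 or higher. There is one reduction step: a participant who meets the criteria again afterwards gets no more drug.
- Section 3: "with allowance for a 50% dose reduction for adverse events as specified in section 5.6".
- Section 13.1 foresees participants being "placed on a reduced dose of 300 mg/week because of intolerance to drug due to acne".
- Section 13.4 introduces the supporting analysis with "Because of the required dose modification to 300 mg".
- Section 7.3, Day 8 Visit, for toxicity under the rule given earlier in the protocol: "study staff will instruct the participant on their modified study dose (3 tablets) for day 8 and 15".

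Three other provisions bear on the consequences. Section 7.3 adds that the "Day 8 clinic visit is optional". Section 5.7.1 states: "Compliance (tablet ingested/tablet instructed to take) will be assessed". Section 5.2 states: "A single bottle containing 16 tablets of study agent will be dispensed"; Section 6.6 adds that 24-tablet bottles stay in use until repackaging is done.

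**The concern.** Section 7.3 relies on the same toxicity rule as Section 5.6 but prints a different tablet count. The wrong figure sits in the procedure staff follow when telling a participant what to take, and it errs towards more drug for someone who has just had a toxicity that calls for halving the dose.

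The single reduction step adds to this. A participant put on 450 mg who met the criteria again would be stopped without ever having received the 300 mg level that the protocol provides.

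There is a smaller effect on data. Compliance is tablets taken over tablets instructed, so its denominator depends on which section the site followed. The supporting analysis in Section 13.4 relates EGFR phosphorylation to dose received, and it would then contain two reduced doses where the plan expects one.

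**Working it through.** **Inputs.** Tablet strength 150 mg (Sections 5.1 and 6.1); full dose 4 tablets; reduced dose 2 tablets (Section 5.6) or 3 tablets (Section 7.3); bottle of 16 tablets (Section 5.2) or, for now, 24 (Section 6.6); 30 participants planned on erlotinib (Section 13.3).

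**The plan's own figure.** Dose = tablets × 150 mg; reduction = 1 − dose/600.

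- Section 5.6: 2 × 150 = 300 mg; 1 − 300/600 = 50%. This agrees with the 50% in Section 3 and the 300 mg in Sections 13.1 and 13.4.
- Section 7.3: 3 × 150 = 450 mg; 1 − 450/600 = 25%. This agrees with none of them.

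Ratio per reduced dose: 450/300 = 1.5.

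**Course total for a participant reduced from Day 8.**

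| | Section 7.3 | Section 5.6 | Ratio |
|---|---|---|---|
| Three doses, tablets | 4+3+3 = 10 | 4+2+2 = 8 | 1.25 |
| Three doses, mg | 1500 | 1200 | 1.25 |
| Four doses (surgery on Days 23-28), tablets | 4+3+3+3 = 13 | 4+2+2+2 = 10 | 1.30 |
| Four doses, mg | 1950 | 1500 | 1.30 |

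The unreduced three-dose total is 1800 mg.

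**Supply.** The largest total, 13 tablets, fits in a 16-tablet bottle, so nobody would run short under either count. After three doses the tablets left are 16 − 10 = 6 against 16 − 8 = 8, or 14 against 16 from a 24-tablet bottle.

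**Compliance.** A site that instructs and scores by the same section gets a correct ratio. If the two are mixed over three doses, a participant who takes 2 tablets at each reduced dose but is scored against 3 gets 8/10 = 80%; one who takes 3 and is scored against 2 gets 10/8 = 125%.

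**Number affected.** The documents give neither the rate of dose-modifying toxicity by Day 8 at 600 mg weekly nor attendance at the optional visit. Assuming 5-20% and 50-100% among the 30 erlotinib participants, the range is 30 × 0.05 × 0.5 = 0.75 to 30 × 0.20 × 1.0 = 6. Placebo participants could receive the same instruction under the blind, but it would carry no excess drug.

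**The case against.** The best defence is that the governing rule is clear. Section 5.6 is the dedicated section, Section 3 defers to it by number, and Section 7.3 itself points back to the rule. The two reminder calls in Section 7.3 also cover dose modifications and print no tablet count. A participant told 3 tablets still takes less than the assigned 600 mg, and Section 2.2 reports that weekly dosing up to 1600 mg did not define a maximum tolerated dose. The site worksheets are not in the documents and may already say 2.

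This shows which figure is intended and limits the likely harm. It does not make 3 tablets correct, and staff who read an explicit count in the visit procedure have little reason to look elsewhere.

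Some narrower objections stand. The 80% and 125% compliance values need a site to instruct by one section and score by the other, which nothing in the protocol directs, and Section 13.6 keeps pill counts out of the primary analysis. The returned count differs by 2 tablets, so reconciling it against Section 5.6 could reveal the error, though only after the doses were taken. The 1-to-6 range rests on assumptions alone and should not decide how serious the point is.

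**Conclusion.** The contradiction is real, and Section 7.3 must be corrected. Four sections agree on a halved dose and none defines a 450 mg step. The continued use of 24-tablet bottles hints at a former six-tablet dose, half of which would be 3 (24 tablets over four doses is 6 each), but that is inference and the conclusion does not need it.

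The firm result is arithmetic: 450 mg instead of 300 mg at each reduced dose, and 25% more drug over three doses for an erlotinib participant reduced from Day 8. The point is serious because it is a wrong dosing instruction for people with toxicity. It does not threaten the trial's validity: the sample size, the as-randomized primary comparison and the by-arm toxicity comparison are unchanged, and the supporting analysis can use the dose actually taken if it is recorded.

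**What to change.** In Section 7.3, Day 8 Visit, change the count from 3 tablets to 2, or delete it and refer to Section 5.6 so that the figure stands in one place only. Send the sites a memo. Check that the Day 8 source documents and the compliance worksheet use 2 tablets as the instructed reduced dose. For anyone already told 3, record both the instructed and the actual counts, so that compliance and the dose-received measure reflect what happened.

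The cost is a one-word protocol correction and a memo, with no change to sample size, randomization or analysis.

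### Section 7.3 gives the reduced dose at the Day 8 clinic visit as 3 tablets (450 mg); Sections 3, 5.6, 13.1 and 13.4 make it 2 tablets, 50% or 300 mg

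*Combined protocol and SAP*

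**What the plan says.** The full dose is four 150 mg tablets (600 mg) once weekly for three doses (Section 5.1). The reduced dose appears in five places.

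- Section 5.6, the dose-modification section: "Study drug will be dose reduced (by 50%) from 4 tablets to 2 tablets for any of the following events".
- Section 3, in its list of the two arms: "Erlotinib (with allowance for a 50% dose reduction for adverse events as specified in section 5.6".
- Section 13.1, explaining the 1:2 allocation, expects that some patients may be "placed on a reduced dose of 300 mg/week because of intolerance to drug due to acne".
- Section 13.4, introducing the supporting analysis: "Because of the required dose modification to 300 mg for grade 2 rash or diarrhea".
- Section 7.3, under the Day 8 visit: "study staff will instruct the participant on their modified study dose (3 tablets) for day 8 and 15".

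Section 7.3 also states that the "Day 8 clinic visit is optional". Participants who opt out are assessed by phone after they have taken the Day 8 dose. The reminder calls before Day 8 and before surgery mention dose modifications but give no tablet count.

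**The concern.** Section 7.3 is the procedural text for the visit at which a coordinator assesses toxicity and tells the participant how many tablets to take next. It gives a different number from the rule it is meant to apply, and the error runs in the less safe direction: a participant who has just met a toxicity criterion gets a smaller cut than intended.

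Day 8 is a plausible time for that decision. Section 6.2 gives a median time to rash onset of 8 days in a lung cancer study, although that was at 150 mg daily, so it is only a guide.

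The routine adherence measure would not reveal the error. Section 5.7.1 defines it this way: "Compliance (tablet ingested/tablet instructed to take) will be assessed". A participant told to take 3 tablets who takes 3 scores 100%, as does one told to take 2 who takes 2. Only the returned-tablet count in Section 5.7.2 would show the difference.

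**Working it through.** **Inputs.** Tablet strength 150 mg and full dose 4 tablets (Section 5.1). Reduced dose 2 tablets (Section 5.6) or 3 tablets (Section 7.3). Three doses as standard, with a fourth if surgery moves to days 23–28 (Section 5.2). Bottles hold 16 tablets, or 24 until repackaging is complete (Section 6.6).

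**1. Reproduce the plan's figure.** 2 × 150 = 300 mg, and 300/600 = 50%. This agrees with Sections 3, 5.6, 13.1 and 13.4.

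**2. Section 7.3.** 3 × 150 = 450 mg, and 450/600 = 75%, a 25% cut. This agrees with none of the four.

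**3. Ratio per reduced dose.** 450/300 = 1.5.

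**4. Cumulative dose, erlotinib arm, reduced from the Day 8 dose onward.**

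| | Section 7.3 | Section 5.6 | Ratio |
|---|---|---|---|
| Three doses | 600 + 450 + 450 = 1500 mg | 600 + 300 + 300 = 1200 mg | 1.25 |
| Four doses, if the reduced count carries over | 600 + 3 × 450 = 1950 mg | 600 + 3 × 300 = 1500 mg | 1.30 |

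Against a full course of 3 × 600 = 1800 mg, the three-dose totals are 83% and 67%.

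**5. Would it be seen?** Over three doses the participant takes 4 + 3 + 3 = 10 tablets or 4 + 2 + 2 = 8. The compliance ratio is 10/10 or 8/8, which is 100% either way. Returned tablets are 6 against 8 from a 16-tablet bottle, or 14 against 16 from a 24-tablet bottle.

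**6. Which section governs?** Section 3 names 5.6 as the place where the reduction is specified. Section 7.3 itself relies on toxicity criteria set out earlier in the protocol, and those criteria are in 5.6. Section 7.3 is therefore the one to correct.

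**7. Grade 4 (secondary).** Section 5.6 applies the 50% cut to any event of grade 3 or higher, whatever its attribution. Its only mandatory stop comes when the criteria are met again after a reduction. Section 11.1.3 defines grade 4 as life-threatening. Read literally, the default in 5.6 after a first grade 4 event is therefore half the dose.

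**The case against.** The contradiction itself has no good defence, but its consequences are easily overstated. A reader might draw any of the following inferences.

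- **That participants are overdosed.** They are not. 450 mg is below the 600 mg starting dose, and Section 2.2 reports that weekly dosing up to 1600 mg did not define a maximum tolerable dose. The fault is a reduction that stops short.
- **That every reduced participant is affected.** The 3-tablet figure appears only in the text for the optional Day 8 clinic visit. A site may also follow 5.6 correctly despite 7.3.
- **That the number affected can be estimated.** The protocol gives no reduction rate at 600 mg weekly. The rates it does give (6% of lung patients reduced for rash, Section 6.2; 5 of 20 bladder patients reduced or held, Section 2.3) come from daily dosing. A count would also need guesses about the share decided at the clinic visit and the share of sites following 7.3. I give none.
- **That the supporting analysis would confuse the two reduced doses.** Section 13.4 says "we will explore a relationship for EGFR phosphorylation with a measure of dose received", and Section 13.6 assigns pill counts to that analysis. A measure built on tablets taken separates 10 from 8. Pooling would occur only if dose were coded as reduced or not, which the protocol nowhere says.
- **That investigators must re-dose after a grade 4 event.** Section 8.3 allows stopping for a medical contraindication or an event that would compromise surgery. Section 8.4 lists adverse events and physician decision as off-study reasons. Section 11.2.2 requires a call to the medical monitor within 24 hours of learning of a serious event. None of these mandates a stop, so the literal reading of 5.6 stands, but clinical judgement is not blocked.

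These limits narrow the consequences. They do not reconcile 3 tablets with 2.

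**Conclusion.** Section 7.3 is wrong as written. For a participant whose dose is reduced at the Day 8 clinic visit, following it gives 450 mg instead of 300 mg per dose, and 1500 mg instead of 1200 mg over three doses. The size rests only on the tablet strength and on staff following 7.3 rather than 5.6. The milligram figures apply to the erlotinib arm. The error does not alter the sample size or the as-randomized primary comparison. It should be corrected because it is an operational dosing instruction that errs in the less safe direction.

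The missing mandatory stop for grade 4 is a lesser, optional improvement. The documents give no rate for related grade 4 events at this dose, and stopping is already permitted.

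**What to change.** **Required.** In Section 7.3 change *3 tablets* to *2 tablets* and add *per Section 5.6*. Correct any visit guide or source form that repeats the 7.3 figure. This is one word and a cross-reference, with no downside.

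**Optional.** Leave the reduction line in Section 5.6 for events of grade 3 or higher as it stands, and add: *except that any grade 4 event at least possibly related to study drug requires permanent discontinuation (off agent per 8.3, remains on study)*. The existing line should not be narrowed to grade 3. Doing so while adding a stop only for related grade 4 events would leave a grade 4 event judged unrelated or unlikely with neither a reduction nor a stop, which is weaker than the present text. The addition is wording only and needs no extra visits or patients. It does not cost a fully dosed participant either, since Section 5.6 already halves the dose of anyone with such an event.
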